
 • 18–45 years old • BMI ≥ 30 kg/m² • Willingness to maintain current diet and lifestyle for the duration of study participation (e.g., agree not to start any special diets or lifestyle changes intended to modify weight) 	
Weight/diet
 
 • Weight change >5 kg within 3 months prior to randomization • Nonstandard diet (e.g., Paleo, Atkins, raw diet, macrobiotic diet) • Significant change in physical activity or diet within 1 month of randomization 
Medical/psychiatric conditions
 
 • History of any of the following medical conditions: 
 ○ Cardiovascular disease, prolonged QT on EKG at screening visit ○ Clinically significant gastrointestinal disorder ○ Bariatric surgery (except for participants with a history of laparoscopic adjustable gastric band surgery) ○ Bleeding disorder ○ Untreated thyroid disease ○ Malignancy within 5 years of screening visit (except for basal cell carcinoma or squamous cell carcinoma) ○ Epilepsy ○ Any significant illness or condition that the investigator determines could interfere with study participation and impact data collection or participant safety • History of an eating disorder or psychosis • Current psychiatric disorder (unless on stable dose of anti-depressant or anti-anxiety treatment for ≥ 6 months with no active symptoms that would qualify for an active psychiatric diagnosis as assessed by the Mini-International Neuropsychiatric Interview) • Substance use disorder active within the last 6 months or clinical suspicion of ongoing substance use disorder at screening visit (based on history, Mini-International Neuropsychiatric Interview, and/or lab results) • Current smoking or tobacco use • Allergy to lidocaine 
Medications
 
 • Medication changes within 4 weeks of enrollment • Oral contraceptives • Use of prescription or over-the-counter drugs or dietary/herbal supplements affecting metabolism, blood glucose, or appetite (metformin allowed if on stable dose with stable weight for ≥ 3 months) 
Screening labs
 
 • Hematocrit $>2\%$ below normal • Fasting glucose >125 mg/dL or hemoglobin A1c $\geq 7\%$ • Liver transaminases (ALT, AST) >2.5 times upper limit of normal • Creatinine >1.5 mg/dL • Hyponatremia 
Further exclusion criteria
 
 • Contraindications to MRI and/or DXA • Pregnancy or breastfeeding • Unwilling to use a medically acceptable form of contraception throughout the study period (female of child-bearing potential only) • Participation in any clinical study involving an investigational drug, device, or biologic within 1 month of randomization

Abbreviations: BMI, body mass index; EKG, electrocardiogram; ALT, alanine transaminase; AST, aspartate transaminase; MRI, magnetic resonance imaging; DXA, dual-energy X-ray absorptiometry.

Table 2. Study procedures at individual study time points.

Assessments	Screen	BL		ON-T (oxytocin versus placebo)				OFF-T
		BL1	BL2	W2	W4	W6	W8	W14
Screening and safety								
• Medical history and physical exam, MMSE	X	X	X	X	X	X	X	X
• Screening/safety labs (CBC, TSH, urine drug screen (at screen only); CMP, HbA1c)	X		X	X	X		X	X
• EKG	X			X			X	
• M.I.N.I.	X							
• Adverse events monitoring, review of concomitant medication, pregnancy test (urine/serum hCG) in females	X	X	X	X	X	X	X	X
Anthropometric measurements (height, weight, %IBW ^a , BMI ^b , WHR ^c)								
	X	X	X	X	X	X	X	X
Energy expenditure, body composition, and fat metabolism								
• Indirect calorimetry (REE)		X				X	X	
• DXA (total fat mass, lean body mass)		X					X	
• MRI (abdominal and thigh measures)		X					X	
• 1H-MRS (liver fat)		X					X	
• Fat biopsy		X		X				
Caloric intake								
• Breakfast test meal (experimental assessment of caloric intake)		X				X		
• 4-day food record (typical eating)		X	X		X	X	X	X
• 24-hr food recall (caloric intake immediately preceding visit)		X	X		X	X		
Laboratory assessments								
• Blood for metabolic profile (e.g., insulin sensitivity, lipid panel, hsCRP, appetite-regulating hormones), gonadal steroids, leukocyte RNA, DNA (optional)			X	X	X	X	X	X
• 24h urine (e.g., cortisol, creatinine)		X					X	
• Stool (e.g., microbiome; optional)			X		X		X	
• Hair (e.g., cortisol; optional)			X				X	
Neuroimaging								
• Food cue task (fasting and post-meal): VTA, OFC, anterior insula, hypothalamus			X		X			
• Impulse control tasks (Stop-Signal Task; Multi-Source Interference Task [optional]) (fasting): dPFC, dACC, preSMA			X		X			
• Handedness questionnaire		X						
Psychological, behavioral, and quality of life assessments								
• Physical activity (PPAQ ^d)	X				X	X		X
• Appetite (VAS ^e), eating behavior and attitudes (EDEQ ^f , DEBQ ^g , EADES ^h , TFEQ ⁱ)		X	X		X	X	X	X
• Reward-related food motivation (BIS/BAS ^j , CTT ^k , PFS ^l) and reward-related behaviors and choices			X		X			X

(Probabilistic Reward Task and Social Reward Task, TEPS ^m ; optional)					
• Impulse control and compulsivity (Delay Discounting Task, Reversal Learning Task, BIS-11 ⁿ , BOCS ^o , SRS ^p ; optional)		X		X	
• Social-emotional functioning (DAPP-BQ ^q , ISEL ^r , LSAS ^s , RMET ^t , SAAM ^u , TAS-20 ^v)	X				X
• Mood and anxiety symptoms (BDI-II, STAI-trait)		X		X	X
• Quality of life (SF-36)		X		X	X
Adherence					
• Study drug diary			X	X	X

Footnotes (including brief definition and reference) and abbreviations:

^aIdeal body weight is determined using elbow breadth and frame size and the 1983 Metropolitan Life Insurance Height/Weight Tables [58].

^bBody mass index is calculated as weight in kg / (height in m)².

^cWaist-to-hip ratio is Iliac circumference over broadest hip circumference.

^dPaffenbarger Physical Activity Questionnaire (interview conducted by trained research coordinators) measuring physical activity [59].

^eVisual Analogue Scales (self-report) asking for subjective appetite [60].

^fEating Disorder Examination Questionnaire (self-report) screening for eating disorders [61].

^gDutch Eating Behavior Questionnaire (self-report) measuring restrained, emotional, and external eating [62].

^hEating and Appraisal Due to Emotions and Stress (self-report) questionnaire assessing stress coping in relation to eating [63].

ⁱThree Factor Eating Questionnaire (self-report) measuring cognitive restraint of eating, disinhibition, and hunger [64].

^jBehavioral Inhibition System/Behavioral Activation System (self-report) assessing motivation regarding aversive/appetitive stimuli [65].

^kCookie Taste Test (behavioral task, post standardized meal and snack) assessing reward-related food motivation beyond satiety [24,66].

^lPower of Food Scale (self-report) measuring appetite for palatable foods [67].

^mTemporal Experience of Pleasure Scale (self-report) measuring anticipatory and consummatory facets of pleasure [68].

ⁿBarratt Impulsiveness Scale (self-report) assessing attentional, motor, and non-planning impulsiveness [69].

^oBrief Obsessive-Compulsive Scale (self-report) measuring the presence of obsessive-compulsive symptoms [70].

^pSelf-Regulation Scale (self-report) capturing attentional control in goal pursuit [71].

^qDimensional Assessment of Personality Pathology-Basic Questionnaire (self-report) assessing suspiciousness and secure attachment [72].

^rInterpersonal Support Evaluation List (self-report) assessing perceived availability of social support [73].

^sLiebowitz Social Adjustment Scale (self-report) measuring fear and avoidance of social situations [74].

^tReading the Mind in the Eyes Test (behavioral task) assessing theory of mind [75].

^uState Adult Attachment Measure (self-report) capturing attachment insecurity [76].

^vToronto Alexithymia Scale (self-report) measuring the ability to describe and identify emotions [77].

BL, baseline visit; T, Treatment; W, week of visit; HR, heart rate; MMSE, Mini-Mental Status Exam; CBC, complete blood count; TSH, thyroid stimulating hormone; CMP, comprehensive metabolic panel (including liver [alanine/aspartate transaminase] and renal [creatinine] function tests, electrolytes [potassium, sodium], and glucose); HbA1c, hemoglobin A1c; EKG, electrocardiogram; M.I.N.I., Mini-International Neuropsychiatric Interview; hCG, human chorionic gonadotropin; REE, resting energy expenditure; DXA, dual-energy X-ray absorptiometry; MRI, magnetic resonance imaging; 1H-MRS, magnetic resonance spectroscopy; hsCRP, high-sensitivity C-reactive protein; VTA, ventral tegmental area; OFC, orbitofrontal cortex; dlPFC, dorsolateral prefrontal cortex; dACC, dorsal anterior cingulate cortex; preSMA, anterior portion of the supplementary motor cortex; BDI, Beck Depression Inventory; STAI, State Trait Anxiety Inventory; SF-36, 36-Item Short Form Survey.

Table 3. Characteristics of the randomized participants at baseline (BL1 visit).

Characteristic	Mean (SD) or N (%)
Demographics	
N randomized	61
Biological sex: F M	33 (54.10%) 28 (45.90%)
Age (years)	33.58 (6.22)
Race	
• Asian	6 (9.84%)
• Black	13 (21.31%)
• White	38 (62.30%)
• Other/More than one race	3 (4.92%)
• Asked but unknown	1 (1.64%)
Ethnicity	
• Hispanic/Latino ethnic group	12 (19.67%)
Clinical characteristics	
BMI (kg/m ²) [F M]	37.02 (4.93) [37.77 (4.92) 36.13 (4.87)]
BMI distribution (kg/m ²)	
• ≥30 to <35 [F M]	24 (39.34%) [8 16]
• ≥35 to <40 [F M]	21 (34.43%) [15 6]
• ≥40 [F M]	16 (26.23%) [10 6]

Abbreviations: F, female; M, male; BMI, body mass index.

Figures

[figure not shown]

Figure 1. Proposed model of oxytocin effects on eating behavior and metabolism leading to weight loss.

Intranasal oxytocin may reduce body weight via multiple complementary mechanisms. Oxytocin may suppress caloric intake via reduced activation of reward and homeostatic brain regions and increased activation of cognitive control brain regions. Oxytocin reduces inflammation, which in turn may reduce appetite and increase energy expenditure. Oxytocin increases thermogenesis and energy expenditure. These effects lead to lipolysis, fat oxidation, and reduced fat mass, ultimately resulting in weight loss.

[figure not shown]

Figure 2. Study design.

Abbreviations: IU, international unit; REE, resting energy expenditure; BL, baseline visit; W, week of visit.

Order of analyses

Randomized, double-blind, placebo-controlled clinical trial

Participants: F/M, 18-45 years, BMI ≥ 30 kg/m²

Randomization at BL: 1 : 1 oxytocin : placebo

Stratification: Biological sex, BMI

1 – Endpoints

Variable	Use/Objective	Variable type	Statistical model	Methods for missing data
Change(%) in body weight (Δ_{W8-BL})	Primary endpoint	Continuous	Mixed-model regression for repeated measurements (MMRM), adjustment for multiple comparisons as appropriate via approach of Hothorn, Bretz, and Westfall	Modified intention-to-treat approach (mITT), Multiple imputation (MI) where applicable
REE (adjusted for lean mass) (Δ_{W8-BL})	Key secondary endpoint	Continuous		
Total body, visceral, and liver fat mass (Δ_{W8-BL})	Key secondary endpoint	Continuous		
Caloric intake (Δ_{W6-BL} , Δ_{W8-BL})	Key secondary endpoint	Continuous		
Metabolic profile (Δ_{W8-BL})	Secondary endpoint	Continuous		
Psychological, behavioral and quality of life assessments	Secondary endpoint	Continuous	Descriptive statistics	
Vital signs, QTc on EKG, %IBW, BMI, waist-to-hip ratio	Vital signs, EKG, anthropometrics	Continuous		
Age, biological sex, race, ethnicity, coexisting conditions, medication	Demographic and clinical variables	Continuous/Categorical		

2 – Mediators

Mediator variable	Dependent variable	Independent variable	Statistical model
Brain activation (Δ_{W4-BL}): food reward, homeostatic and cognitive control regions	Caloric intake (Δ_{W6-BL})	Treatment (oxytocin vs. placebo)	Regression-based mediation analysis
Caloric intake (Δ_{W6-BL})	Change(%) in body weight (Δ_{W8-BL})	Treatment	
REE (Δ_{W6-BL})	Change(%) in body weight (Δ_{W8-BL})	Treatment	

3 – Safety and Compliance (all study time points)

Variable	Use/Objective	Variable type	Statistical model
N (%) of in-trial period treatment-emergent adverse events (AE), AE-related discontinuations	Safety endpoint	Categorical/Count	χ^2 test (oxytocin vs. placebo) for severity categories (mild, moderate, severe)
N (%) of total expected study drug doses administered per subject	Treatment adherence	Count	Descriptive statistics: N (%) with compliance $\geq 80\%$

4 – Off-treatment follow-up (W14)

Variable	Use/Objective	Variable type	Statistical model
Body weight, anthropometrics, caloric intake, metabolic profile, psychological, behavioral and quality of life assessments, safety	Follow-up (sustained effects) and safety	Continuous	Descriptive statistics, MMRM (separate analysis)

Figure 3. Proposed statistical analysis plan.

Abbreviations: F, female; M, male; BMI, body mass index; BL, baseline visit; W, week of visit; REE, resting energy expenditure; QTc, QT corrected; EKG, electrocardiogram; IBW, ideal body weight.

For study endpoints, main contrasts are stated (e.g., Δ_{W8-BL}); further contrasts may be investigated as appropriate and according to assessment time points of endpoint variables (Table 2).

Declaration of interests

The authors declare that they have no known competing financial interests or personal relationships that could have appeared to influence the work reported in this paper.

The authors declare the following financial interests/personal relationships which may be considered as potential competing interests:

[name] served on the scientific advisory board and has a financial interest in OXT Therapeutics, Inc.

[name] also received funding for an investigator-initiated study by Tonix Pharmaceuticals.

All other authors declare no conflicts of interest.

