¹¹ Division of Women's Health, Department of Medicine and Department of Psychiatry, Brigham and Women's Hospital and Harvard Medical School, Boston, MA, USA.

Abstract

Background: Obesity affects more than one-third of adults in the U.S., and effective treatment options are urgently needed. Oxytocin administration induces weight loss in animal models of obesity via effects on caloric intake, energy expenditure, and fat metabolism. We study intranasal oxytocin, an investigational drug shown to reduce caloric intake in humans, as a potential novel treatment for obesity.

Methods: We report the rationale, design, methods, and biostatistical analysis plan of a randomized, double-blind, placebo-controlled clinical trial of intranasal oxytocin for weight loss (primary endpoint) in adults with obesity. Participants (aged 18–45 years) were randomly allocated (1:1) to oxytocin (four times daily over eight weeks) versus placebo. Randomization was stratified by biological sex and BMI (≥ 30 to < 35 kg/m², ≥ 35 to < 40 kg/m², ≥ 40 kg/m²). We investigate the efficacy, safety, and mechanisms of oxytocin administration in reducing body weight. Secondary endpoints include changes in resting energy expenditure, body composition, caloric intake, metabolic profile, and brain activation via functional magnetic resonance imaging in response to food images and during an impulse control task. Safety and tolerability are assessed biweekly and at a 6-week follow-up after treatment completion.

Results: Sixty-one male and female participants aged 18–45 years were randomized (mean age 34 years, mean BMI 37 kg/m²). The study sample is diverse with 38% identifying as non-White and 20% Hispanic.

Conclusion: Investigating intranasal oxytocin's efficacy, safety, and mechanisms as an anti-obesity medication will advance the search for optimal treatment strategies for obesity and its associated severe sequelae.

Keywords: Obesity; Oxytocin; Weight loss; Appetite regulation; Energy metabolism; Neuroimaging

1. Introduction

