Oxytocin is a nine amino acid peptide hormone produced by neurons in the paraventricular and supraoptic nuclei of the hypothalamus, secreted directly into brain regions involved in energy homeostasis and appetite regulation, and released into the bloodstream by the posterior pituitary gland [10–12]. Oxytocin neurons project to anorexigenic arcuate nucleus proopiomelanocortin neurons critical for regulation of energy balance, as well as the ventral tegmental area (VTA) and nucleus accumbens responsible for reward-related eating behavior. Further, oxytocin has been shown to mediate anorexigenic actions of leptin and cholecystokinin (CCK). See Figure 1 for a working model of obesity-related pathophysiology and proposed neural and metabolic oxytocin effects. Animal studies have shown that oxytocin may drive weight loss and result in sustained weight reduction by different mechanisms [13–15]. In rodents and non-human primates with diet-induced obesity, oxytocin administration prevents the physiological decrease in REE occurring with weight loss [13,16–18]. Oxytocin induces lipolysis resulting in reduced adipocyte size and decreased subcutaneous, visceral, and liver fat while preserving lean mass [13,15,17,19,20]. Exogenous oxytocin increases fat utilization [21] and might even induce conversion of white adipose tissue into thermogenic “beige” adipocytes [15]. Acute oxytocin administration reduces caloric consumption [22,23], particularly of palatable foods [24,25], whereas oxytocin antagonists have the reverse effect [26]. Further, oxytocin reduces cortisol levels and inflammation, which may, in turn, reduce caloric intake and improve metabolism [10,12].

In humans, proof-of-concept investigations show that acute intranasal oxytocin administration reduces food intake in both healthy men and women and those with obesity [21,25,27,28], potentially through modulation of neural processing in brain regions related to reward, energy homeostasis, and cognitive control [29–31]. Perturbations in these neural pathways may underly the development of obesity [32,33]. Intranasal oxytocin is well-tolerated by humans with minimal adverse events [34]. A clinical trial in a small sample of non-diabetic individuals with obesity (n=9 in the oxytocin arm) reported a significant BMI reduction after 8-week treatment with 24 international units (IU) (4 times/day) of intranasal oxytocin compared to placebo [35]. While the

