findings are promising, this pilot study was small and did not assess mechanisms or safety. More extensive clinical trials are needed.

2. Methods

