We will conduct regression-based mediation analyses to explore mechanisms underlying the proposed effects of intranasal oxytocin treatment: We will investigate whether (a) the change in brain activation in key reward-related food motivation (VTA, OFC, anterior insula) and homeostatic (hypothalamus) regions during fasted and fed states as well as in cognitive control-related regions (dlPFC, dACC, preSMA) during the fasted state from baseline following 4-week oxytocin treatment mediates change in caloric intake at a test meal 6 weeks from baseline, (b) the change in caloric intake at 6 weeks from baseline mediates the percentage change in body weight at 8 weeks from baseline, and (c) the change in REE at 6 weeks from baseline mediates the percentage change in body weight at 8 weeks from baseline.

Safety and compliance endpoints (assessed at each study time point) will be reported and tested for between-group (oxytocin versus placebo) differences. Endpoints regarding the off-treatment follow-up study time point (week 14 visit) will be reported and analyzed using MMRM in relation to baseline and end of treatment (week 8 visit) time points where appropriate (separately from on-treatment analyses).

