2.6. Study drug, study drug administration, and treatment adherence

The study drug, 24 IU of intranasal oxytocin (Syntocinon[®] Nasal Spray, Mylan, Switzerland) or placebo (containing the same inactive ingredients as Syntocinon[®]), is applied as 3 sprays per nostril, 4 times per day (20–30 minutes before main meals and at bedtime), for an 8-week treatment period. We used the same intranasal oxytocin dose (24 IU) in our prior studies of men showing significant effects on food reward, homeostatic, and cognitive control-related

neurocircuits, impulsivity, and caloric intake [21,29,30,56]. Further, this oxytocin regimen (versus placebo) significantly reduced weight in a small study of 20 adults with obesity [35]. In the latter pilot study, as well as in a review article of 38 randomized controlled trials (n = 926 participants) administering up to 40 IU of intranasal oxytocin (4 times/day) over up to 13 weeks [57], no serious adverse events were reported and there were no differences in adverse events between oxytocin and placebo groups.

To assess treatment adherence, we ask participants to complete and return a drug diary at each visit during the 8-week treatment (Table 2). Adherence is determined per the drug diary reflecting $\geq 80\%$ study drug administration. Drug accountability is assessed by study staff throughout the study, and subjects are asked to return all used and unused study drug at each visit.

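### The only adverse-event test named is a chi-square over severity categories; run as an arm-by-severity table it would not compare how many participants have adverse events, and no test is given for AE-related discontinuations

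*Combined protocol and SAP*

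**What the plan says.** Figure 3, part 3 (Safety and Compliance) lists the safety variable as "N (%) of in-trial period treatment-emergent adverse events (AE), AE-related discontinuations", typed as categorical or count. The statistical model given for it is a chi-square "test (oxytocin vs. placebo) for severity categories (mild, moderate, severe"). No level for participants without an AE is listed, and it is not stated whether events or participants are counted, or over what denominator.

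Section 2.5.3 adds: "Safety and compliance endpoints (assessed at each study time point) will be reported and tested for between-group (oxytocin versus placebo) differences". It names no method. Section 2.3 says that AE severity is graded by CTCAE v5.0 and that expectedness and relationship are evaluated. The week 14 row of Figure 3 lists safety among continuous variables under descriptive statistics and MMRM, which is not a comparison of AE frequency. No other AE comparison appears.

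There are hints about the unit. N (%) counts participants in Table 3 and in the adherence row of the same part ("Descriptive statistics: N (%) with compliance" of at least 80%), and a discontinuation happens once per person. A participant reading is therefore plausible, but it is not stated.

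**The concern.** Safety is a declared objective ("We investigate the efficacy, safety, and mechanisms of oxytocin administration in reducing body weight"), and the Introduction says of the earlier trial that "this pilot study was small and did not assess mechanisms or safety". When section 2.6 sums up prior safety evidence, it does so as a comparison between groups: "no serious adverse events were reported and there were no differences in adverse events between oxytocin and placebo groups". Readers will expect this trial to make the same kind of statement.

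A chi-square on a table with only mild, moderate and severe columns leaves out everyone without an AE. It asks whether the severity profile differs between arms, not whether AEs are more common in one. Choosing participants as the unit does not cure this, because participants without an AE still fall outside the table. Nor can a severity table compare how often participants discontinue because of an AE, although discontinuations share the same row. At stake is that the one specified safety p-value could be reported as no difference in AEs when it did not test that.

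**Working it through.** The plan gives no AE rate, power or sample size for this comparison, so there is no stated figure to reproduce.

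**Inputs.** 61 participants randomized 1:1 (section 2.2). Arm sizes are not given; 31 and 30 are assumed. A two-sided alpha of 0.05 is stated for the power calculation (section 2.5.1) and assumed here. AE incidence and severity mix are assumptions. All tests are Pearson chi-square without continuity correction, the sum of (O − E)²/E; intervals are Newcombe 95% CIs.

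**Worked example, each participant at worst grade.** Arm A (31): mild 16, moderate 6, severe 2, none 7. Arm B (30): 8, 3, 1, none 18. The mix is the same in both arms by construction.

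1. *2x3 table, no 'none' column.* Row totals are 24 and 12, column totals 24, 9 and 3, sum 36. Expected counts in arm A are 24×24/36 = 16, 24×9/36 = 6 and 24×3/36 = 2, equal to the observed counts. Chi-square = 0 on 2 df, p = 1. Moving any one arm A participant to a different grade gives p between 0.86 and 0.96.
2. *Any AE against none.* 24/31 = 77.4% and 12/30 = 40.0%. Expected AE counts are 31×36/61 = 18.30 and 30×36/61 = 17.70; expected counts without an AE are 12.70 and 12.30. Each cell deviates by 5.70, so chi-square = 5.70²×(1/18.30 + 1/17.70 + 1/12.70 + 1/12.30) = 8.83 on 1 df (unrounded inputs), p = 0.003. Risk difference 37 points (95% CI 13 to 56).
3. *Worst grade with a 'none' column (2x4).* Chi-square 8.83 on 3 df, p = 0.032.
4. *Alternative reading: one participant-level test per category, whole arm as denominator.* Mild 16/31 against 8/30, p = 0.046; moderate 6/31 against 3/30, p = 0.30; severe 2/31 against 1/30, p = 0.57.

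**Simulation.** 20,000 trials per setting, 31 and 30 participants, severity mix 75/20/5% in both arms. Share of trials with p < 0.05:

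| Incidence | 2x3, no 'none' | Worst grade with 'none' | Any AE |
|---|---|---|---|
| 20% vs 40% | 3.9% | 26% | 41% |
| 30% vs 60% | 3.8% | 50% | 66% |
| 40% vs 80% | 3.9% | 80% | 91% |

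With equal incidence (20 to 70%) the 2x3 test rejects in 2.9 to 3.5% of trials. Doubling the incidence therefore barely moves it. A separate simulation with a 6:2:1 mix gave 4.5 to 4.7% for the 2x3 test, even at 90% against 30%.

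**The case against.** The strongest reply is that the plan never says 2x3. The wording could mean a comparison of N (%) within each severity category, and if N counts participants over the whole arm, those without AEs are included. On the example above the mild comparison would then give p = 0.046 rather than 1. This stands, and it makes the point conditional on the reading. But the plan does not state that version. It would still give no overall AE comparison, and its three unadjusted tests carry a 7.6 to 11.0% chance of at least one p < 0.05 when nothing differs (incidence 20 to 70%). No version of a severity test compares AE-related discontinuations.

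It is also fair that section 2.5.3 shows the intent to compare the arms, that the counts are to be reported, and that section 2.7 describes an independent data and safety monitoring board. A reader who sees 24/31 against 12/30 would not be misled by p = 1. This limits the harm but does not make the named test suitable.

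The example holds the severity mix equal on purpose. It shows what the test cannot see, not what is likely; a drug that also shifted the mix would give the 2x3 test some power.

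A reader might further infer that counting events inflates false positives. That needs events as the unit and severity that clusters within a person, neither of which the documents state. The paper also expects few events ("Intranasal oxytocin is well-tolerated by humans with minimal adverse events"), and at an assumed 0.5 AEs per person the simulated false-positive rate is only 4 to 7%. The point does not rest on it.

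**Conclusion.** The point holds as a conditional one and merits a change before analysis. As the cell is most literally read, the only named AE test compares severity mix and has essentially no power for a difference in how many participants have AEs: it rejects in about 4% of trials when incidence doubles, against 41 to 91% for any AE versus none. That blindness when the mix is equal does not depend on the assumed rates; the particular p-values and power figures do, as they do on the assumed 31 and 30 split. The lack of a suitable test for AE-related discontinuations holds on every reading.

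A reader might conclude that the plan will hide an excess of AEs, or that it definitely specifies an invalid test. The documents support neither: counts are to be reported, and a per-category participant analysis is a possible intent. What they show is one terse cell from which two analysts could run materially different tests, one of which does not answer the safety question. The primary analysis is not touched.

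**What to change.** In Figure 3, part 3, and section 2.5.3:

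- State that the participant is the unit and that all participants in the arm form the denominator.
- Compare the arms on the proportion with at least one treatment-emergent AE and on the proportion with AE-related discontinuation, each with a risk difference and 95% CI.
- Tabulate each participant's worst CTCAE grade by arm, including a 'none' row.
- Report total event counts by arm descriptively.

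The cost is wording only, since AEs are already graded by CTCAE and can be tabulated by participant. There are two downsides. Worst grade discards repeat events, which is why event counts should still be shown. Intervals also stay wide at 61 participants: 6/31 against 6/30 with any AE gives −21 to +19 points, and 2/31 against 1/30 discontinuations gives −11 to +18 points. Those widths are a reason to lead with estimates and intervals, so that a non-significant result is not taken as evidence of equal safety.
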